### **9.1.1. Incidence of TEAEs**

Summaries of the total number of TEAEs and the number and percentage of subjects with at least one TEAE will be provided. The number and percentage of subjects and the number of events will also be presented by SOC and PT. At each level of subject summarization, a subject is counted once within each PT if the subject reported one or more events.

The summary of TEAEs will also be presented in descending order from the SOC with the highest total incidence (that is, summed across all treatment groups) to the SOC with the lowest total incidence. If the total incidence for any two or more SOCs is equal, the SOCs will be presented in alphabetical order. Within each SOC, the PTs will be presented in alphabetical order.

An additional summary will be presented by PT only. This summary will be presented in descending order from the PT with the highest total incidence to the PT with the lowest total incidence.

All AEs will also be presented in a listing.

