3.1.1. Placebo-Controlled Treatment Period

During the placebo-controlled treatment period, a total of approximately 76 subjects with FSHD1 will be randomized 1:1 to receive 15 mg PO of losmapimod (n=38) or placebo (n=38) tablets BID for 48 weeks.

At the time of this protocol amendment (10 April 2020), enrollment was completed. A total of 80 subjects have been enrolled. Twelve subjects had rolled over to the OLE portion of the study at Week 24, prior to the COVID-19 pandemic (under protocol version 3.0). At their next clinic visits, these 12 subjects will follow the assessments for the Week 36 visit followed by the Week 48 visit in the placebo-controlled portion of the study under the COVID-19 Pandemic Emergency protocol version 4.0. These subjects will continue to receive open-label losmapimod during this time.

Subjects will participate in the placebo-controlled treatment period for approximately 53 weeks, including the following:

- a 4-week screening period: Day -28 until Day -1 before the first study drug administration
- a 48-week placebo-controlled treatment period
- for subjects who choose not to roll over into the OLE, a safety follow-up visit 7 days (± 3 days) after the last dose of study drug (OLE visits and procedures are described in Section 3.1.2)

The 12 subjects who rolled over to the OLE portion of the study at Week 24, prior to the COVID-19 pandemic (under protocol version 3.0), participated in the placebo-controlled portion of the study for approximately 29 weeks including the following:

- a 4-week screening period: Day -28 until Day -1 before the first study drug administration
- a 24-week placebo-controlled treatment period
- for subjects who chose not to roll over into the OLE, a safety follow-up visit 7 days (± 3 days) after the last dose of study drug (OLE visits and procedures are described in Section 3.1.2)

During the placebo-controlled treatment period, subjects will be asked to attend the study clinic at each scheduled visit (Table 2). Study drug (losmapimod or placebo) will be administered BID and should be taken with food.

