3.1.2. Open-Label Extension

Once subjects reach Week 48, they will have the option to roll over into the OLE, with all subjects receiving 15 mg PO losmapimod tablets BID. Subjects who wish to roll over into the OLE must complete all procedures from the Week 48 end of placebo-controlled treatment period/start of OLE visit (Table 2).

Subjects will remain in the OLE until 90 days after commercial drug is available post regulatory approval or until the study is discontinued by the sponsor. All subjects who complete or discontinue from treatment will complete a safety follow-up visit 7 days (± 3 days) after the last dose of study drug.

During the OLE, subjects will attend clinic visits approximately every 12 weeks (Table 3). Study drug (open-label losmapimod) will be administered BID and should be taken with food.

Blood samples for PK (losmapimod concentration) will be collected after dosing at the Week 144 clinic visit, preferably ≥ 1 hour after dosing.

Safety and tolerability will be evaluated based on the assessment of AEs, AESIs, SAEs, laboratory tests, ECGs, vital signs, and physical examinations.

The full schedule of assessments for the OLE is provided in Table 3. Scheduled visits may be split over 2 days if required, with a maximum of 5 business days in between visits. Unscheduled visits may be performed if clinically indicated.

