### 4.1. Analysis Periods

For the purposes of efficacy and safety data analysis, and for reporting, two analysis periods for post baseline data are defined: placebo-controlled treatment period and OLE. The placebo-controlled treatment period encompasses data through Week 48 or Week 24 for subjects who prior to the COVID-19 pandemic had the option to roll over into the OLE at Week 24. The OLE encompasses all losmapimod data starting a day after the Week 48 visit or Week 24 visit for subjects who prior to the COVID-19 pandemic had the option to roll over into the OLE at Week 24. The duration of OLE is defined for each subject as the time after completion of the Week 48 or Week 24 for subjects who prior to the COVID-19

pandemic had the option to roll over into the OLE at Week 24 through completion of the safety follow-up after the end of treatment or discontinuation of the study.

In addition, a supplementary analysis period will be considered which is the losmapimod exposure period that encompasses all losmapimod exposure data, irrespective of when the losmapimod exposure starts (i.e., baseline or OLE).

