#### **4.8. Sample Size**

The sample size for OLE is determined by the number of subjects anticipated to roll over from the placebo-controlled treatment period. A total of 80 subjects have been enrolled in the placebo-controlled treatment period which is 4 subjects higher than the planned sample size of 76 subjects.

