## 7.2. Study Treatments

### 7.2.1. Extent of Exposure

The duration of exposure to losmapimod is the total number of days a subject is exposed to losmapimod; this duration is the interval from the first dose date of losmapimod to last dose date of losmapimod (ie, calculated as the date of last dose of losmapimod minus the date of first dose of losmapimod + 1). If the last dose date of losmapimod is missing, or if a subject is lost to follow-up, but the drug accountability log confirms that the subject has taken losmapimod, the visit date following the last completed drug accountability log will be used.

The exposure to losmapimod will also be characterized by cumulative dose, which is defined as the cumulative number of losmapimod tablets taken in the placebo-controlled treatment period and OLE.

The duration of exposure to losmapimod will be summarized for all subjects who entered OLE using summary statistics according to the sequence of actual treatment received in combination with entry point of OLE. For the Placebo BID/Losmapimod 15 mg BID column, only the duration of exposure while on losmapimod will be summarized. The duration of exposure will then be classified into the following categories: < 8 weeks, >= 8 weeks, >= 16 weeks, >= 24 weeks, >=36 weeks, >=48 weeks, >=60 weeks, >=72 weeks, >=84 weeks, >=96 weeks, >=108 weeks, >=120 weeks, >=132 weeks, >=144 weeks, >=156 weeks, >=168 weeks, >=180 weeks, >=192 weeks, >=204 weeks, and >=216 weeks and will be presented as the number and percentage of subjects in each duration category.

The total cumulative dose for losmapimod in mg will be defined as the total number of losmapimod tablets taken across all study days times 7.5 mg if 2 tablets were given while times 15 mg if 1 tablet was given. Average daily dose of losmapimod will be defined as cumulative dose of losmapimod divided by total days on losmapimod. The average daily dose and cumulative dose will be summarized using summary statistics according to the sequence of actual treatment received in combination with entry point of OLE. For the Placebo BID/Losmapimod 15 mg BID columns, only the cumulative dose and average daily dose for losmapimod will be summarized.

A summary of each subject's exposure to losmapimod will also be presented in a listing.

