An overview summary of the number and percentage of subjects with any TEAE, serious TEAE, study drug-related TEAE, study drug-related serious TEAE, TEAE leading to treatment discontinuation, TEAE leading to study withdrawal, and AE leading to death throughout the duration of the study will be provided. An TEAE is considered as study drug-related if the relationship assessment provided by the investigator is “Possibly Related”, “Probably Related”, “Definitely Related”, or missing.

In addition, the number and percentage of subjects with at least one AESI will be presented. Adverse events of special interest for this study include liver tests that meet the criteria for potential drug-induced liver injury (DILI) in accordance with the US Food and Drug Administration (FDA) “Guidance for Industry-Drug-Induced Liver Injury: Premarketing Clinical Evaluation”. Further details of liver tests and criteria are described in [Section 9.2.2](#).

A separate presentation, unless otherwise specified, will be provided for TEAEs that occurred during the placebo-controlled treatment period and OLE. A total column will be presented for tables showing TEAEs during the OLE.

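### TEAE tables for the controlled period and the open-label extension carry no person-time, so they cannot separate a changed event rate from longer observation

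*SAP*

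**What the plan says.** Safety and tolerability of long-term treatment is the OLE primary endpoint (Protocol 7.2.1; SAP 3.2.1). On incidence, SAP 9.1.1 states that "Summaries of the total number of TEAEs and the number and percentage of subjects with at least one TEAE will be provided". It gives subjects and events again by system organ class and preferred term. SAP 9.1 adds: "A separate presentation, unless otherwise specified, will be provided for TEAEs that occurred during the placebo-controlled treatment period and OLE". The table list (SAP 14.4) accordingly has, for each summary, one table through the data cut, one for the OLE and one for the controlled period (14.3.1.1.1 to .3, 14.3.1.2.1 to .3, 14.3.2.1.1 to .3). Columns are treatment sequence by OLE entry point (SAP 4.2), with a total column in the OLE tables.

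Most subjects have "a 48-week placebo-controlled treatment period" (Protocol 3.1.1), but "Twelve subjects had rolled over to the OLE portion of the study at Week 24, prior to the COVID-19 pandemic". For analysis, "The OLE encompasses all losmapimod data starting a day after the Week 48 visit or Week 24 visit" (SAP 4.1). Its end is open: "Subjects will remain in the OLE until 90 days after commercial drug is available post regulatory approval" or until the sponsor stops the study (Protocol 3.1.2). SAP visit windows run to Week 216 and beyond.

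Exposure has its own summary: "The duration of exposure to losmapimod is the total number of days a subject is exposed to losmapimod" (SAP 7.2.1). It is not linked to the adverse event tables. Neither SAP 9.1 to 9.1.7 nor Protocol 7.6.6 plans an exposure-adjusted rate, a time-to-first-event estimate or incidence over equal-length intervals.

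**The concern.** A count of events, or the share of subjects with at least one, grows with observation time even when the risk per unit of time is constant. Here the two periods are reported in matching tables but differ greatly in length. A reader asking whether adverse events became more or less frequent with long-term dosing, or differ from time on placebo, will turn to these tables. They cannot answer, because a higher OLE figure may reflect a higher rate or only longer follow-up. The cut date is not fixed either (SAP 11.1), so the figures move with each cut. The SAP already annualises change for most of the MRI and functional measures (% change per year, SAP 8.1 to 8.2.3) but does nothing comparable for the primary safety endpoint.

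**Working it through.** **Plan's own figures.** The documents give no expected TEAE rate for this trial, so there is no planned figure to reproduce. The only overall adverse event percentages come from earlier repeat-dose studies (Protocol 1.4). They reproduce: 815/1327 = 61.4% and 406/735 = 55.2%.

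**Inputs.** "A total of 80 subjects have been enrolled in the placebo-controlled treatment period" (SAP 4.8); 12 of them had 24 controlled weeks and 80 − 12 = 68 were scheduled for 48. Week 216 counts from Day 1, so it means 216 − 48 = 168 OLE weeks for the main group and 216 − 24 = 192 for the early roll-overs.

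**Assumptions.** The hazard is constant and the same in both periods. All 80 subjects enter the OLE and are followed to the cut. The share of subjects affected in 48 weeks, p, is not in the documents and is varied over 5%, 10% and 20%.

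**Exposure.** Mean controlled weeks: (68×48 + 12×24)/80 = 44.4. Mean OLE weeks at a Week 216 cut: (68×168 + 12×192)/80 = 171.6. The ratio is 3.9, and under a constant rate expected event counts scale by the same factor.

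**Percentages.** P(t) = 1 − (1 − p)^(t/48), weighted 68:12. For p = 10%:

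- Controlled: (68×10.0% + 12×5.1%)/80 = 9.3%.
- OLE: (68×30.8% + 12×34.4%)/80 = 31.4%.

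| p in 48 weeks | Controlled | OLE, Week 72 cut | OLE, Week 144 cut | OLE, Week 216 cut | Rate per 100 subject-years, both periods |
|---|---|---|---|---|---|
| 5% | 4.6% | 2.9% | 10.1% | 16.8% | 5.6 |
| 10% | 9.3% | 5.9% | 19.6% | 31.4% | 11.5 |
| 20% | 18.6% | 12.0% | 37.0% | 54.9% | 24.3 |

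The rate is −ln(1 − p)/48 × 52.18 × 100, so the between-period rate ratio is 1.00 by construction. At Week 216 the percentage ratios are 3.62, 3.38 and 2.96.

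**Attrition.** With an assumed 20% yearly dropout, the OLE share over 168 weeks is λ/(λ+μ) × [1 − exp(−168(λ+μ))], where λ = −ln(1 − p)/48 and μ = −ln(0.8)/52.18. This gives 11.8%, 22.5% and 40.5%, with mean exposure of 120 weeks.

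**Direction.** The gap reverses only when OLE exposure is below about 44 weeks (pooled mean) to 48 weeks (main group). Enrollment was complete by 10 April 2020 (Protocol 3.1.1). Adding 336 days and the 5-day window puts the last on-schedule Week 48 visit at 17 March 2021, or 21 April 2021 if up to 35 days of screening followed enrollment. Subjects still in the study had therefore accrued about 69 to 74 OLE weeks by protocol version 5.0 (16 August 2022).

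**Entry point.** Within the controlled-period tables, a 10% event shows 5.1% in the 24-week columns against 10.0% in the 48-week columns.

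**The case against.** The strongest reply is that these are descriptive tables in a Phase 2 extension. The periods sit in separate tables, no between-period test is planned, and the early roll-overs have their own columns, so their shorter exposure is visible. All of that stands, and it limits the point to what the tables can show.

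A reader might infer several stronger things that the documents do not support:

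- That only percentages are given. Event counts are tabulated too, though they are equally unadjusted.
- That the periods appear as adjacent columns, or that all sequences differ in length. Columns are sequence by entry point, and the two sequences with the same entry point have equal scheduled length.
- That the OLE lasts 216 weeks. Week 216 is a study week.
- That the OLE must look less safe. This depends on the cut, attrition and event frequency; a Week 72 cut would show 9.3% controlled against 5.9% OLE for the 10% event. For very common events the ratio is limited by the ceiling at 100%: with p = 55% it is 51.7% against 94.2%.
- That the needed exposure days already exist. SAP 7.2.1 derives one total losmapimod duration per subject, without placebo days or a split by period.

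Two cautions about rates also stand. A single OLE-wide rate assumes a constant hazard, so it cannot show change within the OLE. The open-label analysis set contains only subjects who completed 24 or 48 controlled weeks (SAP 4.10.1), so its controlled-period rates are survivor-selected. Dividing by subject-years does not cure that.

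**Conclusion.** The point holds as a gap in presentation of the primary OLE endpoint; it does not invalidate any planned inference. Without person-time, the TEAE tables cannot distinguish a changed event rate from longer observation. Under a constant hazard and full follow-up to Week 216, an unchanged rate produces OLE percentages about 3.0 to 3.6 times the controlled-period ones for events affecting 5% to 20% of subjects in 48 weeks. At a Week 144 cut the factor is about 2. These sizes rest on assumed event rates and on the 68:12 split holding among those who rolled over. The qualitative conclusion needs only that mean exposure differs between the periods. The direction, higher in the OLE, needs a cut beyond about one OLE year, which the protocol dates make likely for subjects who stayed in the study.

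**What to change.** In SAP 9.1.1 and Tables 14.3.1.1.x, 14.3.1.2.x and 14.3.2.1.x, keep the counts and percentages and add:

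- Subject-years at risk, events per 100 subject-years, and subjects with a first event per 100 subject-years (time stopped at the first event in that period).
- A breakdown by period and treatment received (placebo; losmapimod in the controlled period; losmapimod in the OLE) and by entry point. In the through-data-cut tables this also separates placebo time from losmapimod time in the placebo/losmapimod columns.
- Preferably, the same rates by equal-length OLE interval, for example 48 weeks, so that a change within the OLE can be seen.
- A footnote that controlled-period rates in the open-label analysis set exclude subjects who did not complete 24 or 48 weeks and are not the randomized safety comparison.

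Derive placebo days and period-specific losmapimod days from dosing dates and the SAP 4.1 period boundaries. State that rates per 100 subject-years are the figures to use when reading across periods. No new data are needed; the cost is SAP wording, a small extra derivation and wider tables.

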### **9.1.2. Relationship of TEAEs to Study Drug**

A summary of TEAEs by maximum relationship to study drug will be presented in a table by incidence of occurrence. The investigator will provide an assessment of the relationship of the event to the study drug. The possible relationships are “Unlikely Related”, “Possibly Related”, “Probably Related”, and “Definitely Related”. In the TEAE by maximum relationship table, if a subject reports multiple occurrence of the same TEAE, only the most related occurrence will be summarized. All AEs that have a missing relationship will be presented in the summary table as “Missing”, but will be presented in the data listing with a missing relationship.

The AE data will be categorized and presented by SOC, PT, and relationship in the same manner as described in [Section 9.1.1](#).

### **9.1.4. Serious TEAEs**

The seriousness of an AE should be assessed independently by the Investigator. An SAE is defined as any untoward medical occurrence that at any dose results in death, is life-threatening, is a congenital anomaly/birth defect, requires in-patient hospitalization or prolongation, or results in significant disability.

Important medical events that may not result in death, be life-threatening, or require hospitalization may be considered SAEs when, based upon medical judgment, they may jeopardize the subject and may require medical or surgical intervention to prevent one of the outcomes listed above.

SAE data will be presented by SOC and PT in the same manner as described in [Section 9.1.1](#).

#### **9.1.5. TEAEs Leading to Treatment Discontinuation**

A summary of TEAEs that caused treatment discontinuation will be presented in a table. At each level of subject summarization, a subject is counted once if the subject reported one or more events.

TEAE leading to treatment discontinuation data will be presented by SOC and PT in the same manner as described in [Section 9.1.1](#).

#### **9.1.6. TEAEs Leading to Study Withdrawal**

A summary of TEAEs that led to study discontinuation will be presented in a table. At each level of subject summarization, a subject is counted once if the subject reported one or more events.

TEAE leading to study discontinuation data will be presented by SOC and PT in the same manner as described in [Section 9.1.1](#).

#### **9.1.7. Death**

A summary of TEAEs where the answer to ‘Outcome’ in the AE form is ‘Death Related to Adverse Event’ will be presented in a table.

Death data will be presented by SOC and PT in the same manner as described in [Section 9.1.1](#).

### **9.2. Clinical Laboratory Evaluations**

Results from laboratory assessments will be summarized over time showing both the placebo-controlled treatment period and OLE data.

### **9.2.1. Hematology**

The following laboratory tests will be included: hemoglobin (including mean corpuscular volume), mean corpuscular hemoglobin, mean corpuscular hemoglobin concentration, hematocrit, red blood cell count, total white blood count, platelet count, differential blood counts, including basophils, eosinophils, neutrophils, lymphocytes, and monocytes.

Summary tables presenting observed values and changes from baseline will be presented for the following hematologic tests: hemoglobin, red blood cell count, hematocrit, total white blood cell count, lymphocyte count, neutrophil count, basophil count, eosinophil count, and platelet count. Changes from baseline to each scheduled post-baseline visit will be presented. All hematology data by subject will also be presented in a listing.

The clinical assessment of ‘Low’, ‘Normal’, or ‘High’ relative to the reference range will be summarized comparing the baseline results to the minimum and maximum values post-baseline in separate shift tables for those subjects with results at both baseline and post-baseline visits.

### **9.2.2. Serum Chemistry**

The following laboratory tests will be included: glucose, sodium, potassium, calcium, inorganic phosphate, total protein, albumin, blood urea nitrogen, creatinine, total bilirubin, alkaline phosphatase (ALP), aspartate aminotransferase (AST), alanine aminotransferase (ALT), gamma-glutamyl transferase, and creatinine phosphokinase.

Summary tables presenting observed values and changes from baseline will be presented for the following serum chemistry tests: direct bilirubin, alkaline phosphatase, aspartate aminotransferase, alanine aminotransferase, and gamma-glutamyltransferase. Changes from baseline to each scheduled post-baseline visit will be presented. All chemistry data by subject will also be presented in a listing.

The clinical assessment of ‘Low’, ‘Normal’, or ‘High’ relative to the reference range will be summarized comparing the baseline results to the minimum and maximum values post-baseline in separate shift tables for those subjects with results at both baseline and post-baseline visits.

Results indicating liver-related abnormalities (i.e., ALT, AST, Total Bilirubin, and/or ALP) will be summarized separately. A newly notable laboratory abnormality is defined as an abnormality observed post baseline that meets the notable criteria in [Table 9-1](#) and that did not exist at baseline. Subjects can still meet the criteria for a newly notable laboratory abnormality if the baseline value is missing. The table below displays the general variables and thresholds of interest. Subjects are considered to have notable laboratory abnormalities if his/her response falls within the specified definitions at least once during the treatment period.

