1.5. BENEFIT/RISK ASSESSMENT

Losmapimod has been widely tested in various subject populations across at least 10 adult indications, including coronary artery disease, rheumatoid arthritis, and COPD. The majority of these studies lasted 24 weeks, with dosing in one study of up to 52 weeks. The safety data from these studies demonstrate satisfactory safety and tolerability; the severe and/or serious events that have been reported were generally specific to the population under study. Thus, COPD and respiratory events occurred in the studies evaluating subjects with COPD. Similarly, serious cardiac events were observed in those studies that evaluated subjects with coronary artery disease. As these events were generally indication specific, the risk of their occurrence in the FSHD population is considered minimal.

Hepatotoxicity

In clinical trials to date, elevations in transaminases have occurred in few subjects among over 3,500 exposures of losmapimod. These have generally been mild, asymptomatic, and reversible, and the majority were confounded by other medications or clinical conditions. In 11 integrated repeat-dose studies in various patient populations, the frequency of liver events was 0.9% in the losmapimod group (further details are presented in the IB). Preclinical data demonstrate reversible increases in rat liver weight with no clinical chemistry or microscopic correlate. However, hepatotoxicity has been observed after repeat dose administration of some p38 MAPK inhibitors. The mechanism of hepatotoxicity for those compounds has not been elucidated and thus applicability to losmapimod is unknown. Exclusion criteria (Section 4.1.2), data collection, and study drug stopping criteria (Section 6.2.1.3) relating to liver tests are well defined.

Renal Function

In clinical studies with losmapimod, a small asymptomatic increase in serum creatinine of 1% to 7% was noted; this increase appeared to attenuate with continued therapy as well as with discontinuation and may be related to inhibition of renal transporters (further details are presented in Section 5.3.2.6.2 of the IB). Individuals with severe renal impairment are excluded from the study (Section 4.1.2). Renal function (Section 6.2.2) and AEs (Section 6.2.1) will be monitored during the trial.

Embryo-Fetal Malformations

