6.2.2. Laboratory Analyses

Samples for serum chemistry, hematology, coagulation, and urinalysis will be collected at the time points specified in Table 2 and Table 3. Processing, storage, and shipping procedures for all clinical laboratory samples are provided in a laboratory manual. Sample collection details are presented in Section 6.7.

For the screening visit, subjects will be required to fast for at least 4 hours prior to laboratory blood samples being taken.

Any abnormal laboratory test results (hematology, clinical chemistry, or urinalysis) or other safety assessments (eg, ECGs, radiological scans, vital sign measurements), including those that worsen from baseline (ie, prior to first dose in the placebo-controlled treatment period) and are felt to be clinically significant in the medical and scientific judgment of the investigator, are to be recorded as AEs or SAEs. However, any clinically significant safety assessments that are associated with the underlying disease, unless judged by the investigator to be more severe than expected for the subject's condition, are **not** to be reported as AEs or SAEs. Clinically significant abnormal laboratory test results will be reviewed by the investigator and recorded as AEs or SAEs on the appropriate page in the eCRF.

Blood and other biological samples will be collected for the following clinical laboratory tests:

Serum chemistry	Glucose, sodium, potassium, calcium, inorganic phosphate, total protein, albumin, blood urea nitrogen, creatinine, total bilirubin, alkaline phosphatase, aspartate aminotransferase, alanine aminotransferase, gamma-glutamyltransferase, creatine phosphokinase
Hematology	Hemoglobin (including mean corpuscular volume), mean corpuscular hemoglobin, mean corpuscular hemoglobin concentration, hematocrit, red blood cell count, total white blood cell count, platelet count Differential blood counts, including basophils, eosinophils, neutrophils, lymphocytes, and monocytes
Coagulation	International normalized ratio, prothrombin time, partial thromboplastin time
Urinalysis	Leucocytes, blood, nitrite, protein, urobilinogen, bilirubin, pH, specific gravity, ketones, glucose If there is a clinically significant positive result, urine will be sent for microscopy and/or culture.
Pregnancy	Serum β -hCG (all female subjects of child-bearing potential), serum follicle-stimulating hormone (suspected postmenopausal female subjects only [defined in Section 5.5.1]), urine pregnancy test

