7.6.6. Safety Analyses

Safety data in the placebo-controlled treatment period will be analyzed using the safety analysis set and summarized by treatment group and visit (if applicable) using descriptive statistics. Safety data in the OLE will be analyzed using the open-label analysis set.

Treatment-emergent AEs will be summarized by MedDRA system organ class and preferred term; separate summaries will be produced for treatment-related AEs, AESIs, SAEs, and discontinuations due to AEs. Laboratory tests, vital signs, findings from physical examinations, and ECGs will be summarized for changes over time during treatment using descriptive statistics.

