### **9.2.3. Urinalysis**

The following urine laboratory tests will be included: leukocytes, blood, nitrite, protein, urobilinogen, bilirubin, pH, specific gravity, ketones, and glucose.

Summary tables presenting observed values and changes from baseline will be presented for the following urinalysis tests: glucose, blood and protein. Changes from baseline to each scheduled post-baseline visit will be presented.

All urinalysis data by subject will be presented in a listing.

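### The SAP's chemistry change-from-baseline table names direct bilirubin, which is in neither test panel, and gives no change row to total bilirubin, which is collected and used in the liver criteria

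*SAP*

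**What the plan says.** SAP 9.2.2 first lists the serum chemistry tests to be included, 15 in all. It then names five for the tables of observed values and change from baseline: these "will be presented for the following serum chemistry tests: direct bilirubin, alkaline phosphatase, aspartate aminotransferase, alanine aminotransferase, and gamma-glutamyltransferase". In SAP 14.4 the matching output is Table 14.3.4.2.1, whose title names no tests.

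The panel in Protocol 6.2.2 ends "creatinine, total bilirubin, alkaline phosphatase, aspartate aminotransferase, alanine aminotransferase, gamma-glutamyltransferase, creatine phosphokinase". It contains total bilirubin and creatinine but not direct bilirubin.

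On liver safety, SAP 9.2.2 adds: "Results indicating liver-related abnormalities (i.e., ALT, AST, Total Bilirubin, and/or ALP) will be summarized separately". Table 9-1 and the potential-DILI definition below it use total bilirubin, as does Protocol 6.2.1.3.

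Two general statements frame the laboratory analysis. SAP 9.2 says: "Results from laboratory assessments will be summarized over time showing both the placebo-controlled treatment period and OLE data". Protocol 7.6.6 says: "Laboratory tests, vital signs, findings from physical examinations, and ECGs will be summarized for changes over time during treatment using descriptive statistics".

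On creatinine, Protocol 1.5 reports from earlier studies that an "increase in serum creatinine of 1% to 7% was noted; this increase appeared to attenuate with continued therapy as well as with discontinuation". It says that renal function will be monitored in this trial.

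**The concern.** A list that fixes the rows of a safety table should draw on tests that are measured. Here one of the five is not in either panel. A programmer who follows the text would produce an empty row, or would have to decide without instruction which test was meant. Meanwhile the bilirubin fraction on which the liver criteria depend would have no summary of its level or change by visit.

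Safety is the primary endpoint of the open-label extension (OLE), so this is a rule for a primary-endpoint output and not background text.

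Creatinine is a lesser matter. The protocol describes a rise with a time course, and a long extension is well placed to describe it. As written, the SAP text names no summary that would show it.

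**Working it through.** No power, alpha or sample-size figure is involved. The check compares lists.

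**1. The two panels.** Protocol 6.2.2 and SAP 9.2.2 each list 15 tests: glucose, sodium, potassium, calcium, inorganic phosphate, total protein, albumin, blood urea nitrogen, creatinine, total bilirubin, ALP, AST, ALT, GGT and creatine phosphokinase. The SAP spells the last two slightly differently. Treating those spellings as the same tests, the panels are identical.

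**2. The five named tests against the panels.**

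| Named for change table | In protocol panel | In SAP panel |
|---|---|---|
| Direct bilirubin | No | No |
| ALP | Yes | Yes |
| AST | Yes | Yes |
| ALT | Yes | Yes |
| GGT | Yes | Yes |

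Four of the five match. Of the 15 collected tests, 15 − 4 = 11 are not named for the change table, among them total bilirubin and creatinine. Direct bilirubin appears nowhere else in either document. The bilirubin in the urinalysis panel is a urine test.

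**3. The sister sections.** In SAP 9.2.1 the change tables "will be presented for the following hematologic tests: hemoglobin, red blood cell count, hematocrit, total white blood cell count" and five further tests, nine in all, and every one is in that section's own list. In SAP 9.2.3 they "will be presented for the following urinalysis tests: glucose, blood and protein", and all three are in that section's list. Across the three sections 9 + 5 + 3 = 17 tests are named. Sixteen come from their own section's list, and direct bilirubin is the one that does not.

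**4. Where total bilirubin still appears.** It is in the by-visit counts of notable liver results (Table 14.3.4.2.3), the by-visit potential-DILI table (Table 14.3.4.2.4) and the chemistry listing (16.2.8.2.1). It may also be in the shift table (14.3.4.2.2), since the text restricts that table to no named tests. The first two report crossings of 2 × ULN, not the level or its change.

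**5. Where creatinine still appears.** It is in the listing and possibly in the shift table. The shift table compares the baseline category (Low, Normal or High) with the post-baseline minimum and maximum, so it carries no visit dimension. It is also insensitive to a small rise. Taken alone, a 7% rise moves a subject from Normal to High only if the baseline exceeds 1/1.07 = 93.5% of the upper limit. For a 1% rise the figure is 1/1.01 = 99.0%. It cannot show whether a rise persists or attenuates.

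**The case against.** The strongest reply is that very little is lost. One row of one table is affected. Total bilirubin is covered by every output that applies a liver criterion, and no liver-safety conclusion hangs on a mean-change row. That stands, and it limits the size of the point. It does not make the rule executable: the text still asks for a test that is not listed as measured.

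A second reply is that this is an obvious slip for total bilirubin. It may be, but the documents do not say so. The table shells are a separate document, and direct bilirubin could conceivably be reported by the laboratory. The request should therefore allow for either answer.

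On creatinine, a reader might infer that leaving it out breaks the protocol's commitment to summarise laboratory tests over time. The documents do not support that. Protocol 7.6.6 names no tests, and the SAP also selects subsets for hematology and urinalysis. The chemistry list reads as a liver panel, in keeping with the only adverse event of special interest named, potential DILI. The monitoring statement in Protocol 1.5 points to Section 6.2.2, which covers sampling and investigator review and promises no mean-change table. The protocol also calls the rise small and asymptomatic, and possibly related to renal transporter inhibition. Chemistry is sampled at every OLE visit, and the creatinine data are listed. All of this stands. What remains is that no named summary can show the time course the protocol itself describes.

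**Conclusion.** The inconsistency is certain on the text: one of five named chemistry tests is in neither panel, and total bilirubin, which is in both and drives the liver criteria, has no change-from-baseline row. This is an analysis rule that is wrong as written, with a small and contained effect. Adding creatinine is a recommended improvement, not the correction of a departure.

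A reader might go further and infer that bilirubin or renal safety goes unreported in the OLE. That would be wrong, since both tests are collected and listed and total bilirubin is summarised against its threshold by visit.

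The conclusion assumes that the two panels list everything measured and that Table 14.3.4.2.1 follows the 9.2.2 text. If the shell already shows total bilirubin, the SAP text still needs correcting to agree with it.

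**What to change.** In SAP 9.2.2, reconcile the list for observed values and changes with the collected panel. Name total bilirubin in place of direct bilirubin. If direct bilirubin is shown to be collected, add total bilirubin to the list instead and include direct bilirubin among the section's listed tests. Check that the shell for Table 14.3.4.2.1 matches.

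As an improvement, add creatinine to the same table.

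The cost is one corrected row, one additional row and a shell check. Total bilirubin and creatinine are already collected, so no new sampling is needed.
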